230 subjects total (100 each group). This extra 30 subjects will allow for screen failures that occur on the study for example change in plans from use of ETT or LMA to nasal cannula in the procedure room after subjects may have been consented. They will not be randomized and need to be replaced on the study.

2. What is the statistical or other justification for the total number of subjects described above?

Sample sizes of 75 per group achieve 80% power to detect a difference of 2 mmHg between the null hypothesis that both group mean EtCO₂ measurement over the length of the monitoring period are 37.2 mmHg and the alternative hypothesis that the mean of the CO₂ group is 39.2 with an estimated within group standard deviation of 4.3 mmHg and with a significance level (alpha) of 0.05 using a two-sided two-sample t-test. To adjust for the possibility of a 25% drop out rate 100 patients per group will be enrolled.

We have also allowed 30 extra subjects due to some screen failures we have had.

5. Gender of the Subjects

A. Are there any enrollment restrictions based on gender?

No

6. Age Range of Subjects

A. Will adults be enrolled ?

Yes

1. What is the age range of the adult subjects?

The adults in this study will be 19 years old.

2. What is the rationale for selecting this age range?

As we were enrolling subjects into this study we noticed we had several 19 year old subjects still being seen by our GI Department. Therefore, they would qualify for the study. We did

not want to exclude them from participating in the study. The research will be conducted in children aged 6 months to 19 years to determine if end tidal CO₂ remains persistently elevated in intubated children undergoing upper endoscopy with CO₂ insufflation and to determine if there are changes in minute ventilation with CO₂ use during upper endoscopy.

B. Will children (18 years of age or younger) be included in this research?

Yes

1. What is the justification for inclusion of children in this research?

The research will be conducted in children aged 6 months to 18 years to determine if end tidal CO₂ remains persistently elevated in intubated children undergoing upper endoscopy with CO₂ insufflation and to determine if there are changes in minute ventilation with CO₂ use during upper endoscopy.

2. What is the age range for the child subjects, and what is the justification for selecting this age range?

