6 months to 18 years. The justification for this age range is that carbon dioxide is increasingly used for insufflation in pediatric endoscopy. Though there is an increase in its use, the deleterious effects of carbon dioxide insufflation and absorption in this age group are not known. This highlights the importance on further studies in this age group to determine if this elevated end tidal CO₂ level can be avoided by intubation, if there are changes in the minute ventilation with CO₂ use and if it is physiologically significant and should be used with caution.

3. Will this study enroll wards of the state?

No

7. Race and Ethnicity

Are there any subject enrollment restrictions based upon race or ethnic origin?

No

8. Vulnerable Subjects

A. Will prisoners be included in the research?

No

B. Select from the list all of the vulnerable populations that will specifically be recruited to participate in this research.

Decisionally-impaired persons

Critically ill patients

Students of the investigator
Employees of the investigator
Educationally disadvantaged individuals
Socially or economically disadvantaged individuals
Individuals with a stigmatizing illness or condition
Individuals from a marginalized social or ethnic group
Other.
♦ No vulnerable subjects will be specifically recruited

9. Inclusion Criteria

What are the specific inclusion criteria?

- Children 6 months to 19 years old undergoing upper endoscopy in CHMC whose parents or legal guardians consent to the study will be included.

10. Exclusion Criteria

What are the specific exclusion criteria?

- Patients and legal guardians who decline participation in the study and patients with chronic respiratory disease (defined as severe asthma, bronchopulmonary dysplasia and cystic fibrosis related pulmonary disease) will be excluded from the study.
Patients with cyanotic heart disease and those with ASA status of ≥ 3 .
- Patients who are wards of the state or in foster care will be excluded as well
- Prisoners will be excluded
- Patients undergoing colonoscopy only procedures or procedures not related to upper endoscopy will be excluded

11. Pregnancy and Contraception Requirements

A. Are women of child bearing potential (WOCBP) included in this research?

Yes

a. Are there any specific contraception requirements for subjects?

No

1. Provide justification for absence of contraception requirements

There are no interventions that are likely to be of risk to a fetus

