Each envelope will contain 25 cards marked "Air" and 25 cards marked "CO2" ; Therefore, there will be a total of 100 cards marked "Air" and 100 cards marked "CO2" in all the 4 sets of envelopes

After it has been determined that the patient can be included in the study and the consents have been signed; the procedure nurse will open the first envelope and randomly pick either CO₂ or Air. She will then set up the insufflation gas based on the gas picked. She will cover the air and CO₂ dispensing machine so that the patient, anesthesiologist and endoscopist are all blinded to the type of insufflation gas used during the procedure. She will complete randomization using the cards in each set of envelope before moving to the next set. The endoscopy room/procedure room nurse will keep a record of patients randomized into the air or CO₂ group in a locked cabinet. She will assign arbitrary letters or numbers to the gas

used so that the biostatistician who will perform the interim analysis will be blinded to the arm of study as well.

We will perform an interim analysis after enrolling 100 patients (50 patients in the Air group and 50 patients in the CO₂ group)

D. Identify:

1. All procedures, interventions, evaluations and tests performed solely for research purposes (eg, administration of an investigational drug or a new psychological assessment instrument; randomization)

The consenting process for the study is only done for research purposes. Also, the only other procedures that would be performed solely for research purposes is the randomization of enrolled patients to air or CO₂ gas for insufflation during the endoscopic procedure. Although, air is the standard insufflation agent for endoscopy in pediatrics; many centers now routinely use carbon dioxide given the vast data in adults showing decreased abdominal discomfort and distension with carbon dioxide use.

In our center, we routinely use CO₂ for colonoscopy and most endoscopists use air for upper endoscopy.

2. All procedures, interventions, evaluations and tests performed for clinical indication but more frequently than they would be if the subject was not participating in the research (eg, extra blood tests; additional radiology exams)

There will be no extra blood tests or additional radiology exams

E. Describe briefly the statistical methods used to analyze the data (or reference the appropriate section of the detailed protocol or grant).

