Is there the prospect for direct benefit (eg, research on diagnosis or treatment of disease)?

Yes

Describe potential benefits to the subjects that may reasonably be expected from participation in the research, if any. If there are therapeutic and non-therapeutic components of the research, address anticipated benefits to subjects that may reasonably be expected from each of these components.

Patients randomized to the CO₂ arm may benefit from less procedure pain when used during colonoscopy as a few pediatric studies have shown these benefits with the use of CO₂ for colonoscopy.

20. Potential Benefits to Society

Describe the potential benefits to society that may reasonably be expected to result from this research.

Publishing this work may encourage the use of safe and best insufflation practices in all children. If elevated end tidal CO₂ levels persist despite protection of the airway, then CO₂ use in children may be limited or restricted to only colonoscopy.

ALTERNATIVES TO PARTICIPATION

21. Alternatives to Participation

1. Describe the likely care the subject would receive at this institution were he/she not to participate in the research. If there are more than one reasonable courses of treatment briefly describe.

There is currently no standard of care at this institution regarding use of "CO₂" versus "air" as the insufflation gas. The gas of choice to be used is usually at the discretion of the endoscopist and the availability of carbon dioxide gas in the procedure room or OR.

2. Is the potential benefit of the research at least as good as the potential benefits of the alternatives described above?

Yes

3. Are there any reasonably available alternatives outside this institution which would have the potential for providing benefit to the subjects outside the research context?

No

4. Would any of the study procedures or courses of treatment in the protocol be available to the subject if they elected not to participate?

Yes

a. Explain.

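### Combined upper endoscopy and colonoscopy cases are eligible and EtCO₂ is averaged over the whole monitoring period, so the estimate is not specific to upper endoscopy

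*Combined protocol and SAP*

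**What the plan says.** **Who enters.** Section 10 states: "Patients undergoing colonoscopy only procedures or procedures not related to upper endoscopy will be excluded". Section 12.B describes the population as patients whose procedures involve upper endoscopy. A patient having both scopes in one session therefore qualifies. Two other places expect such patients: Section 25.B describes schedulers raising the study when they book EGD/colonoscopy, and Section 19 says patients in the CO₂ arm "may benefit from less procedure pain when used during colonoscopy".

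**Which gas.** Section 12.D.1 describes usual practice: "In our center, we routinely use CO₂ for colonoscopy and most endoscopists use air for upper endoscopy". Section 21 says instead that the institution has no set standard and that the endoscopist usually chooses, subject to availability. Within the trial, Sections 12.B and 12.C have the nurse set up whichever gas was drawn and cover the machine. Section 12.D.1 describes the randomisation as being to a gas for the endoscopic procedure, with no exception for a colonoscopy part.

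**What is measured.** The outcome in the Section 4 sample-size statement is the mean EtCO₂ "measurement over the length of the monitoring period". The abstract has EtCO₂ and minute ventilation (MV) recorded throughout the time in the procedure room. No upper-endoscopy window is defined. Section 12.B collects the reason for endoscopy and the durations of procedure and anaesthesia. It does not list procedure type, segment times or gas by segment. Section 12.E contains no stratification, adjustment or subgroup by procedure type.

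**The concern.** Objectives (i) and (ii) in Section 2 are about upper endoscopy. The hypothesis in Section 3 is that the EtCO₂ rises seen earlier were eructated gas and will disappear once the airway is protected. Gas put into the colon cannot be assumed to reach the EtCO₂ reading by that route; if it raises EtCO₂, absorption is the likelier path. In combined cases the whole-period mean includes the colonoscopy, so a colonic contribution in the CO₂ arm would be read as a failure of airway protection, or as absorption from the upper GI tract.

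The consequence is practical. Section 20 says that if EtCO₂ stays raised despite a protected airway, use of CO₂ in children might be confined to colonoscopy. A mean that includes colonoscopy time cannot cleanly support that conclusion. With the fields now listed, the two segments could not reliably be separated afterwards.

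**Working it through.** **Step 1. The plan's own figure.** All inputs are from Section 4:
- "Sample sizes of 75 per group achieve 80% power to detect a difference of 2 mmHg"
- "the alternative hypothesis that the mean of the CO₂ group is 39.2", against 37.2 mmHg under the null, so δ = 2
- "an estimated within group standard deviation of 4.3 mmHg", so σ = 4.3
- "with a significance level (alpha) of 0.05 using a two-sided two-sample t-test"

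Normal approximation: n = 2(1.960 + 0.842)² × 4.3² / 2² = 2 × 7.85 × 18.49 / 4 ≈ 72.6, so 73 per group. The noncentral t gives 73.5, so 74. Power at 75 per group is 81.3% (normal) or 80.8% (t). Dropout: 75 / (1 − 0.25) = 100. The plan's 75 and 100 reproduce.

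**Step 2. A simple model of the mixture.** Let f be the share of patients with combined procedures and w the share of their monitoring period spent in colonoscopy. Let D_col be the CO₂-minus-air difference during colonoscopy and D_other the difference in the remaining time. Ignoring carry-over, and taking D_other as the same in all patients, the whole-period difference is

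D = (1 − f·w) · D_other + f·w · D_col.

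The documents give neither f nor w. The values below are assumptions, shown as a range.

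**Step 3. Allocated gas used throughout (the more natural reading).** The arms differ only in the allocated gas, so D is a valid randomised contrast. The 2 mmHg in Section 4 is already stated for the whole-period mean, so this source removes nothing from it and power stays at about 81%. What changes is the meaning of D, in which colonoscopy carries weight f·w:

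| f | w | weight of colonoscopy, f·w | D_col needed for D = 2 if D_other = 0 |
|---|---|---|---|
| 0.1 | 0.25 | 0.025 | 2 / 0.025 = 80 mmHg |
| 0.3 | 0.5 | 0.15 | 2 / 0.15 = 13.3 mmHg |
| 0.5 | 0.75 | 0.375 | 2 / 0.375 = 5.3 mmHg |

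In this model, when combined cases are few, colonoscopy can shift the estimate but could hardly produce all of a 2 mmHg difference. When they are common, it could account for much of it. Carry-over from a colonoscopy done first would add to these weights.

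**Step 4. Conditional case: both arms receive CO₂ during colonoscopy.** Then D_col = 0 and, with D_other = 2, D = 2(1 − f·w). Noncentral t, σ = 4.3:

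| f | w | D (mmHg) | power at 75 per group | n per group for 80% |
|---|---|---|---|---|
| 0.1 | 0.25 | 1.95 | 78.8% | 78 |
| 0.3 | 0.5 | 1.70 | 67.2% | 102 |
| 0.5 | 0.5 | 1.50 | 56.5% | 130 |
| 0.5 | 0.75 | 1.25 | 42.4% | 187 |

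These figures apply only if the routine colonoscopy gas displaces the allocation in air-arm patients.

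**The case against.** A reader might infer from Section 12.D.1 that air-arm patients receive CO₂ during a colonoscopy, so that the arms are contaminated and the trial is underpowered. The documents do not support this. The sentence describes usual care. In the trial the nurse sets up the drawn gas, the machine is covered, and no separate gas is named for a colonoscopy part. Section 19 ties the colonoscopy benefit to the randomised CO₂ arm, which makes sense only if the allocation governs the colonoscopy too. The text does not exclude a switch of gas, but nowhere describes one. Section 12.B also points to a flow chart that is not shown in the available text and may settle the matter, so its absence cannot be held against the plan.

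The case against even the narrower point has some force:
- A whole-procedure comparison is a defensible pragmatic choice for a population defined by procedures involving upper endoscopy.
- Objective (iii), on MV, is not worded as limited to upper endoscopy, although the matching hypothesis in Section 3 is.
- Recording is continuous, duration and reason for endoscopy are collected, and Section 12.E contemplates a mixed model over the monitoring period.
- Restricting the window to the upper scope could miss delayed absorption, and does not remove carry-over if the colonoscopy comes first.

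The first and last of these are good reasons to keep the whole-period comparison. They do not make it specific to upper endoscopy, and a mixed model over time cannot separate the segments unless their times and types are recorded.

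**Conclusion.** The point stands as one of specificity, and it should be fixed. Combined cases are eligible, the averaging window is undivided, and the listed data and analyses offer no way to isolate upper endoscopy. On the more natural reading the randomised comparison is valid and power is about 81% at 75 per group. The estimate nevertheless answers a broader question than objectives (i) and (ii) ask and the Section 20 conclusion needs.

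The size cannot be fixed from the documents. Over the assumed ranges, f from 0.1 to 0.5 and w from 0.25 to 0.75, colonoscopy carries 2.5% to 37.5% of the weight in the estimate before any carry-over. The corresponding power range of 78.8% to 42.4% belongs solely to the conditional case in which the allocation is overridden, and should not be reported as an expected loss.

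**What to change.** 1. For each patient, record whether a colonoscopy was done, its order relative to the upper endoscopy, the gas actually used in each segment, and the upper-scope insertion and removal times.
2. Pre-specify an EtCO₂ and MV comparison in upper-endoscopy-only patients. In combined cases, pre-specify one over the upper-endoscopy segment where that segment comes first, which avoids carry-over. Report both beside the whole-period comparison.
3. State whether the random allocation covers the colonoscopy part of a combined procedure.
4. Reconcile Section 12.D.1 (CO₂ routine for colonoscopy) with Section 21 (no institutional standard). Which gas is clinically appropriate is outside this point.

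The cost is a few recorded fields and one added analysis. The upper-endoscopy-only comparison will use fewer patients, and the segment comparison a shorter averaging window, so both will be less precise than the whole-period result.

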Continuous data will be reported as means with standard deviations, or medians with interquartile ranges depending if variable has normal or skewed distribution respectively. Categorical variables will be described by percentages and proportions. Comparisons of continuous data will be performed using the t-test or Wilcoxon signed-ranks test. Categorical variables will be compared using the chisq test or Fishers exact test. A probability value <.05 will be considered significant. Statistical analysis will be performed using SAS 9 statistical software (SAS Institute, Cary, NC) or Graph Pad Prism 7 for Windows (Graph pad Software, San Diego, CA).

Descriptive statistics, including counts and %, means, SD, medians, will be used to summarize patient characteristics, procedural, anesthesia and safety outcomes for the two groups. Patient characteristics, Patient safety outcomes;(MV, EtCO₂), procedural, and anesthesia outcomes will be compared between the groups using the independent sample t-test or Mann-Whitney test or Fishers exact test as appropriate to the data. Changes in these safety outcome measurements across the monitoring period between the two groups using a mixed effects model will be considered

F. Does this study involve the collection of blood, urine, saliva or other human biological material (HBM)?

No

DRUGS, BIOLOGIC DRUGS AND DEVICES

13. Drugs and Biologic Drugs

1. Does this research involve the use of drugs or biologics?

No

14. Devices

1. Does this research involve a medical device(s)?

No

CONFIDENTIALITY AND PRIVACY

15. Confidentiality and Privacy

A. Describe where research data will be stored. Check all that apply.

♦ On a secure server at UNMC, CHMC, Nebraska Medicine, and/or UNO (including REDCap)

On a secure cloud server - Specify the secured cloud serve:

On a firewall protected database accessible through the internet - Specify who has administrative responsibility for maintenance of the server:

On an encrypted, password protected local hard drive

On an encrypted, password protected portable computer

On an encrypted, password protected flash drive

♦ In hard copy

♦ Other Hard copies of the original signed consent and assent forms will be stored in a locked file cabinet, or in a lock briefcase when not in use

a. Please provide justification for use of hard copies

Hard copies of consent and assent are required and are kept as per institutional policy.

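### Section 12.E calls any between-group p<.05 significant without ranking outcomes, although only mean EtCO₂ is sized; with two to six outcomes the chance of at least one false claim is roughly 8% to 26%

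*Combined protocol and SAP*

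**What the plan says.** Section 12.E gives a single threshold: "A probability value <.05 will be considered significant". It then sets the scope of testing: "Patient characteristics, Patient safety outcomes;(MV, EtCO₂), procedural, and anesthesia outcomes will be compared between the groups", by t-test, Mann-Whitney or Fisher's exact test as suits the data. A further longitudinal comparison of the safety outcomes is left open: "Changes in these safety outcome measurements across the monitoring period between the two groups using a mixed effects model will be considered". The section names no primary outcome, gives no order of testing and states no adjustment.

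The only outcome with a sample size is in Section 4 (Accrual, item A.2). The hypotheses there concern "both group mean EtCO₂ measurement over the length of the monitoring period", and the calculation is made "with a significance level (alpha) of 0.05 using a two-sided two-sample t-test". Section 4 does not call this outcome primary, and Section 12.E does not refer back to it.

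MV has standing of its own. It is objective (iii) in Section 2, worded in terms of significant changes, and it has its own hypothesis in Section 3.

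**The concern.** The trial is sized for one question, but the analysis section gives every comparison the same standing. Read as written, a p-value below .05 for MV, for a duration or for a complication rate supports a claim of a CO₂ effect on equal terms with EtCO₂. The 5% in Section 4 describes the risk of a false claim about mean EtCO₂. It does not describe the risk of some false claim from the whole set.

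This matters because Section 32.C expects the results to guide local practice on the safety of CO₂. A reader of the trial report would have no pre-stated basis for telling the planned conclusion from a chance finding.

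The tests on patient characteristics are a smaller, separate matter. Allocation is random, so any difference in pre-procedure characteristics arises by chance and a p-value for it answers no useful question.

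**Working it through.** **The plan's own figure.** Inputs from Section 4: difference 2 mmHg (37.2 versus 39.2), SD 4.3 mmHg, two-sided alpha 0.05, 80% power.

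- Normal approximation: n = 2(z₀.₉₇₅ + z₀.₈₀)²σ²/δ² = 2(1.960 + 0.842)² × 4.3²/2² = 72.6, so 73 per group.
- The t-test solution is 73.5, so 74 per group.
- At the stated 75 per group, t-test power is 80.8%.
- Dropout: 75/(1 − 0.25) = 100 per group.

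The stated 75 and 100 are reproduced to within two patients. They refer to one test at 0.05.

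**Which outcomes to count.** Section 12.E names MV and EtCO₂ as the safety outcomes, so two is the minimum. It adds procedural and anesthesia outcomes without listing them. Section 12.B collects procedure duration, anesthesia duration, and procedural and anesthesia complications, which brings the count to six. Six is an assumption. Patient characteristics are left out, because they precede the gas.

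**Chance of at least one p<.05 when gas has no effect on any outcome.** For k independent tests this is 1 − 0.95ᵏ:

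- k = 2: 1 − 0.9025 = 9.75%
- k = 6: 1 − 0.7351 = 26.5%

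For test statistics with a common correlation ρ, and c = 1.960, it is 1 − ∫[Φ((c − √ρ·u)/√(1−ρ)) − Φ((−c − √ρ·u)/√(1−ρ))]ᵏ φ(u) du. The documents give no correlations, so a range is shown:

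| Outcomes | ρ = 0 | ρ = 0.5 | ρ = 0.8 |
|---|---|---|---|
| 2 (EtCO₂, MV) | 9.75% | 9.1% | 7.8% |
| 6 | 26.5% | 20.7% | 13.9% |

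**Effect of discreteness.** Two of the six are complication outcomes, and Fisher's exact test is conservative for uncommon events. At 75 per arm its true size is 0.2%, 1.5% and 2.7% for assumed event rates of 2%, 5% and 10%. At a 5% event rate, with independence, the six-outcome figure becomes 1 − 0.95⁴ × (1 − 0.015)² = 1 − 0.8145 × 0.9702 = 21%. At 2% and 10% it becomes 19% and 23%.

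**Effect of the remedy on sample size.** One primary test at 0.05 leaves 75 evaluable and 100 enrolled per group unchanged. If EtCO₂ and MV were instead both confirmatory with Bonferroni at 0.025 each, EtCO₂ would need 90 evaluable per group (t-test), and power at 75 would fall to 72.0%.

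**The case against.** The best defense is that the hierarchy is unlabelled but evident. Mean EtCO₂ is the only sized outcome, it is objective (i), and it is the subject of the first hypothesis. Section 20 also ties any restriction of CO₂ use to EtCO₂ staying elevated. This has force as to intent. It does not settle the analysis, because 12.E states a rule for all outcomes and ranks none, and MV has its own objective and hypothesis.

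Four stronger readings are tempting, and the documents do not support them.

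- *The 5% in Section 4 is inflated.* It belongs to the mean EtCO₂ test. Testing other outcomes does not alter that test's error rate at the final analysis.
- *Baseline comparisons add to the false CO₂ effects.* A chance imbalance that precedes the gas is not a CO₂ effect.
- *Twelve outcomes are tested, giving 46% (1 − 0.95¹²).* Reaching twelve requires heart rate, respiratory rate, blood pressure, nausea, vomiting and headache. Section 12.B collects them, but 12.E does not name them as compared outcomes. Independence also fails, since MV is tidal volume times respiratory rate.
- *CO₂ could be restricted on any outcome that crosses .05.* Section 20 links restriction to EtCO₂ alone.

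A fair objection to the remedy is that objective (iii) asks about significant changes in MV, so removing all inference on MV would leave that objective unanswerable as worded. This stands, and the fix allows for it.

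**Conclusion.** The concern holds in a limited form and is worth correcting. Section 12.E allows a significance claim on any of several unranked outcomes, while only mean EtCO₂ is sized. The chance of at least one false claim is at most about double the nominal 5% for the two named safety outcomes (7.8% to 9.75%). It is about three to five times 5% for six outcomes (about 14% to 26%).

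These figures assume no true effect on any outcome, one test per outcome at a true size of 5%, and a common correlation between 0 and 0.8. The six-outcome range also depends on the assumed count, and conservative exact tests for rare complications would lower it.

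The figures apply to the final analysis only. Section 18.E allows early stopping on significant interim results with no separate alpha; that is a different issue and is not included here.

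**What to change.** In Section 12.E:

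- Name the between-arm difference in mean EtCO₂ over the monitoring period as the single primary outcome, tested at two-sided 0.05 with the two-sample t-test used for the sample size.
- Make MV the key secondary outcome. Either test it only if the EtCO₂ test is significant, or report the difference with a 95% confidence interval. Align the wording of objective (iii) in Section 2, and its repeat in the abstract, with the choice made. An interval would also serve the Section 3 hypothesis of no change in MV better than a p-value, since p>.05 does not show absence of change.
- Report all other outcomes as between-arm differences with 95% confidence intervals, labelled exploratory.
- Describe patient characteristics by arm without p-values.

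The cost is a few sentences in 12.E and the matching edit to objective (iii). No extra patients are needed. The downside is small: MV and the other outcomes can no longer be declared significant on their own. The primary test will hold 5% overall only once the interim look is dealt with separately.
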